#### **Youth level mechanisms**

Treatment Attendance (self-report, parent/caregiver report, and collateral information). The Child and Adolescent Services Assessment [CASA] is a self-and parent-report instrument designed to assess at follow-up the use of mental health services for youth across 31 settings including inpatient, outpatient, and informal services. The measure has acceptable psychometric properties. Collateral information on treatment attendance (attendance at first treatment appointment and total number of treatment sessions attended) will also be collected by contacting each juveniles' treatment provider at the 3-month follow-up. A release of information is requested at baseline, for both primary care physicians (PCP) and their MH provider/agency, as part of the court intake process when treatment referrals are made. The Motivation for Youth's Treatment Scale, an 8-item measure, will be used to assess the youth's motivation to engage in treatment at baseline and at follow-up. The total scale and two subscales (Problem Recognition and the Treatment Readiness) produce alpha coefficients of above .80. The baseline MYTS will be completed at the end of the safety planning intervention to screen and address youth and caregiver motivation for treatment. The Barriers to

Treatment Participation Scale, a 44-item measure, will be completed at baseline and 3-month follow-up by caregivers to assess barriers that parents/caregivers experienced since intervention and the role those barriers may play in treatment engagement. Alpha coefficients range from 0.61 to 0.80. Treatment Satisfaction information will be gathered as part of the follow-up qualitative interview. Youth and caregivers will be interviewed about their satisfaction with the suicide intervention as well as treatment referral in the community at the 3-month follow-up.

*Performance of CT Strategies (PCTS) will be used to assess safety planning skills because it is more ecologically valid than a self-report measure. Raters will assess the extent to which participants demonstrated, through their performance of, their reports of the use of, and their stated intentions to continue the use of, safety planning skills based on a prompt to discuss what behaviors they did and continue to do to keep themselves safe. For example, "Did the youth understand and utilize restriction to means; individualized warning signs; specific coping skills; peer and family social supports to help distract from negative thoughts; adult contacts for help; and reasons for living". Each of the areas will be rated on a 0 to 6 Likert-type scale. Ratings of 4 or higher are considered indicative of independent use of the domain assessed by each item (i.e., clear report of the patient's making use of this domain). Three raters, blind to condition, will rate session tapes. Meetings of the entire rating group and pairs of raters will occur periodically to minimize rater drift.*

*We will also specifically ask teens and parents regarding the teen's access to potential means, including firearms, medications (over-the-counter and prescribed), and alcohol.*

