### **Phase I. Open trial and RCT**

**Study overview.** In this treatment development grant, 70 adolescents in Probation will be recruited to participate in the study. The first 10 will participate in an iterative development open trial. Then 60 youth will be randomized to: 1) the screening/brief intervention safety planning intervention, or 2) standard practice.

**Open Trial Design.** A total of 10 youth will be recruited for open trial in order to: a) test the protocol's applicability in Probation, and b) train the mental health counselors in the protocol. We have used this 2 phase approach extensively in prior studies. The open trial will occur in months 5 - 8 after counselor training. The protocol and procedures will be modified as necessary after the first 5 participants and then again after 10 pilots have been run through the protocol and prior to conducting the pilot RCT

[figure not shown]
**Overview of RCT Trial Procedures.** When youth arrive for their first Probation appointment, they are asked to complete the MAYSI/NSSI assessment. Youth who flag in on the MAYSI or NSSI item on this first screen, will be referred by their PO to the mental health counselor who will approach them about participation in the study. If the parent/caregiver consents to the study, the mental health counselor will then meet with the youth, physically separate from the parent/caregiver, to describe study procedures in detail (**including the fact that only youth who are positive on the secondary screen continue in the study**) and obtain juvenile assent without parental presence (see **Human Subjects**). Consenting procedures will also include permission to access court records. All youth will then complete the complete the Self-Injurious Thoughts and Behaviors Interview 2.0 (SITBI-Short Form^91, see below), to more thoroughly assess self-injurious behavior. Families will then be referred back to their PO to complete the secondary screen. If the youth screens in, he/she is then randomized to either standard practice or the safety planning intervention.

Follow-up assessments will also be completed at 1- and 3-months post-baseline to gather data on youth outcomes related to treatment, self-harm, and recidivism. No juvenile will ever be sanctioned by the court for not agreeing or being unable to participate in the research study (see **Human Subjects/Letter of Support**).

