If a juvenile flags in and is in the experimental condition, the safety planning will occur in three stages: 1) the juvenile will meet with a trained mental health counselor to create the safety plan; 2) the juvenile and counselor will meet with the PO and caregiver to share the safety plan and discuss strategies and challenges to implementing the safety plan; and 3) the PO will then contact the current mental health provider or appropriate community mental health clinic to facilitate an outpatient appointment, if the youth is not at immediate risk. In cases where substance use is an issue, the JJS staff member will ask permission of the youth to relay this to the community mental health clinic or current provider.

The Safety Plan intervention, *which consists of the one module from Co-I [name]'s COPES program described above*, incorporate the SITBI responses, which covers both suicidal and nonsuicidal ideation and behavior, to ensure all areas are covered in the Safety Planning process. For example, the SITBI will identify suicide means youth have thought about using. Youth make a list of dangerous items to remove from their surroundings (e.g., alcohol, knives, razors, medications) in order to reduce access to means, identify their warning signs and vulnerabilities that indicate they may become unsafe, generate helpful coping strategies, and identify people that can help them manage negative feelings.

*The safety plan intervention concludes with a section emphasizing completing referrals for outpatient care for those youth. Youth will also complete the 8-item Motivation for Youth's Treatment Scale (MYTS) to facilitate discussion between the counselor and the youth about the youth's current motivation for treatment. At the same time, the caregiver will complete the Barriers to Treatment Participation Scale (BTPS) that will inform the mental health counselor about potential barriers (identified as "often a problem" or "always a problem") and promote discussion during the safety planning with the youth and caregiver about those potentials barriers and generate ideas on how to overcome them.*

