**Brief Intervention Follow-up Phone Call.** One week after the in-person safety planning, the mental health counselor will contact the teen's parent/caregiver to review elements of the safety plan and problem-solve barriers to using the safety plan and engaging in treatment. If the family has not made contact with a treatment provider, the mental health counselor will further assist the family in setting up an appointment. Co-I

[name]'s research with recently incarcerated and suicidal individuals has shown that telephone follow-up intervention is feasible, acceptable, and powerful in building trust and reducing risk among these populations.

**Baseline and Follow-up Assessment.** In order to pilot test a procedure with the greatest potential to be implemented in a large effectiveness trial in the future, we collect all baseline data from information collected routinely and recorded in court records, with the exception of administering the SITBI. Therefore, potential participants will not be paid for the completion of the baseline measures. The consent form will specify that, as part of participating in the study, the MPIs will be allowed to use the baseline data from the RIFC chart.

The follow-up assessment battery was also designed to reduce participant burden and will be scheduled at 1 and 3 months post-intervention. The 3-month follow-up period will allow us to assess a high-risk period for self-injury as well as the typical period of time that adolescents remain in outpatient psychotherapy. Follow up interviews will be conducted in-person and last approximately 1 hour. Juveniles and a caregiver will each be compensated \$30 for the time to complete the 1 and 3-month assessment.

**Protection against Attrition.** We do not anticipate a great deal of attrition at the 1 and 3-month follow-up assessment, based on our prior success in following participants in our other treatment studies. Nonetheless, after the baseline assessment, participants will be educated on the importance of completing the follow-up assessments; provided the date and time of the follow-up appointments, and provided a study contact number to call if contact information changes. Detailed tracking information will be recorded. Our retention strategies will include phone, texting, email, and postal mail contact (e.g., personalized holiday, thank you, and birthday cards). In addition, names of two friends or family members will be requested in the event that research staff is

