### **Phase I: Data Analysis Plan**

Prior to conducting analyses for the project aims, a series of routine procedures will be conducted to ensure the data accuracy/adequacy. All forms will be checked for missing data and all data will be double entered and backed-up daily. Descriptive statistics will be examined for distributional properties of the variables (e.g., normality, internal consistency). The data will be transformed to achieve normality if needed.

We will conduct analyses in an intent-to-treat (as randomized) manner, and examine as primary analyses unadjusted and secondarily adjusted for selected covariates identified above. Masking integrity will be reviewed. ANCOVA (outcome regressed on baseline) methods will be used, and linear mixed effect models will be used to account for non-independence of repeatedly observed outcomes.

We will examine attrition by comparing follow-up assessment completers and non-completers on socio-demographic and baseline data to determine if they differ systematically. Consistent with an intent-to-treat model, we will include all randomized participants in the analyses. Attrition/Missing Data. It is anticipated that less than 20% of subjects will not have follow-up data. We will test for differential attrition across the experimental condition and the baseline comparison. The analyses described below can account for attrition at the follow-up points. We will employ multiple imputation as our primary approach to missing data [138] and will conduct a sensitivity analysis treating all participants lost to follow-up as treatment failures at the point of loss, i.e. assuming no change on their self-injury-related mechanisms or outcomes. If our primary conclusions are similar with and without extreme missing data assumptions, confidence in the findings will be higher.

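### The motivation and barriers scores labelled baseline are taken inside the safety-planning session, after randomization, and the supplied text gives standard-practice families no occasion to complete them

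*Combined protocol and SAP*

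**What the plan says.** **Order of events.** Under Overview of RCT Trial Procedures, families consent, the youth completes the SITBI, and the probation officer runs the secondary screen. Then: "If the youth screens in, he/she is then randomized to either standard practice or the safety planning intervention". The safety-planning session follows, in the experimental arm only.

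**MYTS.** Youth level mechanisms schedules it at baseline and follow-up and fixes the first occasion: "The baseline MYTS will be completed at the end of the safety planning intervention to screen and address youth and caregiver motivation for treatment". Experimental protocol: Safety Planning describes it in the paragraph on how the session concludes, as a form completed "to facilitate discussion between the counselor and the youth about" current motivation.

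**BTPS.** The same paragraph continues: "At the same time, the caregiver will complete the Barriers to Treatment Participation Scale". The form is there to "promote discussion during the safety planning with the youth and caregiver about those potentials barriers". Youth level mechanisms schedules it at baseline and 3 months, "to assess barriers that parents/caregivers experienced since intervention and the role those barriers may play in treatment engagement".

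**What counts as baseline data.** Baseline and Follow-up Assessment states: "we collect all baseline data from information collected routinely and recorded in court records, with the exception of administering the SITBI".

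**Standard practice.** Current standard practice covers screening, referral and a resource packet. It mentions neither scale.

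**Analysis.** Phase I: Data Analysis Plan makes unadjusted analyses primary and adds that "ANCOVA (outcome regressed on baseline) methods will be used". The Primary Aim text lists motivation and a reduction in treatment barriers among the mechanisms, and plans to check whether the instruments show change across the study. The only baseline covariate named for the mixed models is the SITBI.

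**The concern.** A baseline score earns its place in ANCOVA, or in a change score, because treatment cannot have affected it. Here the first MYTS and BTPS scores come after allocation and within the treatment itself. If the session moves motivation or perceived barriers at once, the score labelled baseline already contains part of the effect, and adjusting for it removes that part from the estimate.

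The control arm is a second problem. The supplied text ties both forms to a session that standard-practice families do not attend. Staff could reasonably collect nothing from controls, and such scores cannot be recovered later. With 60 randomized, and assuming equal allocation, that is 30 youth with no starting value.

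At stake are the analyses of two mechanism measures, and the pilot's judgement on whether they suit a larger trial.

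**Working it through.** The plan states no figure on this point, so there is none to reproduce. The first check is of sequence and consistency; the second shows what the timing could do to an estimate.

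**1. Passages side by side**

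| Question | Section | Answer |
|---|---|---|
| When is allocation made? | Overview of RCT Trial Procedures | After the SITBI and secondary screen, before the session |
| When is the first MYTS? | Youth level mechanisms | End of the session |
| When is the first BTPS? | Experimental protocol: Safety Planning | Same time as the MYTS |
| What are baseline data? | Baseline and Follow-up Assessment | Court records plus SITBI |
| When do controls complete either form at baseline? | Current standard practice | Not mentioned |

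Both first scores are therefore post-randomization. Neither belongs to the baseline data set as the plan defines it. The BTPS wording adds a further mismatch: a form about barriers met since the intervention cannot describe a state before it. The BTPS has only two occasions, so the only change it can show runs from in-session to 3 months.

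**2. Effect on an estimate, if controls are measured at an equivalent time**

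Inputs, in SD units:
- d = 0.50, the follow-up difference between arms (assumed).
- s = 0 to 0.5, the shift already present in the experimental arm's first score (assumed).
- rho = .64, the correlation of first score with follow-up. This is the generic autocorrelation in the Power section, which is not specific to these scales; range .3 to .8.

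Formulas:
- ANCOVA = follow-up difference minus slope times first-score difference = d − rho × s.
- Change score = d − s.

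At rho = .64 and s = 0.2, ANCOVA gives 0.50 − 0.64 × 0.2 = 0.372. The change score gives 0.50 − 0.20 = 0.30.

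| s | ANCOVA, rho .3 | ANCOVA, rho .64 | ANCOVA, rho .8 | Change score |
|---|---|---|---|---|
| 0 | 0.50 | 0.50 | 0.50 | 0.50 |
| 0.1 | 0.47 | 0.44 | 0.42 | 0.40 |
| 0.2 | 0.44 | 0.37 | 0.34 | 0.30 |
| 0.5 | 0.35 | 0.18 | 0.10 | 0.00 |

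A simulation at rho = .8, s = 0.3 and d = 0.5 returned 0.260, against 0.50 − 0.8 × 0.3 = 0.26 from the formula.

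**3. If controls have no first score**

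The table does not apply. Neither a baseline-adjusted nor a change comparison between arms can be computed.

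**The case against.** The strongest reply is that no stated analysis must use these scores. Unadjusted comparisons are primary, the ANCOVA sentence is general, and the mixed model of 1- and 3-month outcomes runs without a first MYTS or BTPS. A reduction in barriers could simply mean fewer barriers than in the control arm. This stands, so the harm is conditional. It does not remove the fault: the plan labels a post-randomization score baseline and leaves general language that would admit it.

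A second reply is that the session effect may be small, because both forms prompt the motivation and barriers discussion and so may precede it. That is fair. Adjustment loses power relative to no adjustment only when s exceeds about d × (1 − √(1 − rho²)) / rho, which at rho = .64 is 0.50 × (1 − 0.768) / 0.64 = 0.18. Below that it gains power, but the estimate is still biased.

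A reader might infer three stronger points that the documents do not support.
- *That the sections contradict one another on when the MYTS is given.* The intervention and measures sections broadly agree. The conflict is with the definition of baseline data, and with the BTPS wording.
- *That the two BTPS forms are designed to cover different periods.* The since-intervention wording is attached to both occasions. The supported point is that it does not fit a baseline form.
- *That the no-change sensitivity analysis would credit lost experimental youth with the session effect.* That analysis covers mechanisms and outcomes related to self-injury and applies from the point of loss. Motivation and caregiver barriers are not plainly included.

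Figures and Appendix 3 are not available and could hold a schedule by arm. The control-arm point is therefore limited to the supplied text.

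**Conclusion.** The point holds and should be fixed. The first MYTS and BTPS scores are post-randomization and in-session, do not fit the plan's own definition of baseline data, and have no stated occasion in the standard-practice arm. This rests on the documents' order of events and needs no numerical assumption.

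The size of any bias cannot be derived, because the documents give no value for the session effect. The figures of 0.37 and 0.30 against 0.50 are illustrations. They depend on assumed d and s, a borrowed correlation, and controls measured at an equivalent time, which no section provides.

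The reach is confined to baseline-adjusted or change-based analyses of two mechanism measures. It would be wrong to infer that the trial's main results are compromised. The SITBI is taken before randomization, and the unadjusted primary comparisons and the feasibility and acceptability targets do not use these scores.

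**What to change.** **MYTS.** Give it to youth in both arms after a positive secondary screen and before allocation is revealed, and let the counselor use that completed form in the session. If it cannot be moved, relabel the in-session MYTS as a process measure and compare follow-up scores between arms without a baseline term.

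**BTPS.** Treat the in-session form as a process measure. Compare 3-month scores between arms without a baseline term, and replace the reference to barrier reduction in the Primary Aim text with that comparison.

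**Analysis plan.** State that neither in-session score serves as a baseline in ANCOVA. If the no-change sensitivity analysis is extended to these scales, state that neither in-session score is the value carried forward.

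**Consistency.** Align Baseline and Follow-up Assessment and Youth level mechanisms with these choices, including which arm completes each form and when.

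**Cost.** Moving the MYTS means an 8-item form, a few extra unpaid minutes, one more step between the positive screen and what follows it, and some control-arm exposure to a form that also serves as a discussion tool. Protocol, consent and analysis wording would change. The process-measure option needs wording changes only.

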### **Service-level measures**

Efficiency and quality of treatment linkage. Data regarding treatment coordination and referral for mental health services will be collected from the RIFC and Probation database regarding Probation staff coordination and collaboration with treatment providers in the community upon referral. **Equity** will be measured by examining differences by sex/ racial/ethnic subgroups in the numbers of at-risk youth who receive the intervention, treatment linkage, and fidelity/quality of the safety intervention.

### **Phase I: Data Analysis Plan**

Prior to conducting analyses for the project aims, a series of routine procedures will be conducted to ensure the data accuracy/adequacy. All forms will be checked for missing data and all data will be double entered and backed-up daily. Descriptive statistics will be examined for distributional properties of the variables (e.g., normality, internal consistency). The data will be transformed to achieve normality if needed.

We will conduct analyses in an intent-to-treat (as randomized) manner, and examine as primary analyses unadjusted and secondarily adjusted for selected covariates identified above. Masking integrity will be reviewed. ANCOVA (outcome regressed on baseline) methods will be used, and linear mixed effect models will be used to account for non-independence of repeatedly observed outcomes.

We will examine attrition by comparing follow-up assessment completers and non-completers on socio-demographic and baseline data to determine if they differ systematically. Consistent with an intent-to-treat model, we will include all randomized participants in the analyses. Attrition/Missing Data. It is anticipated that less than 20% of subjects will not have follow-up data. We will test for differential attrition across the experimental condition and the baseline comparison. The analyses described below can account for attrition at the follow-up points. We will employ multiple imputation as our primary approach to missing data [138] and will conduct a sensitivity analysis treating all participants lost to follow-up as treatment failures at the point of loss, i.e. assuming no change on their self-injury-related mechanisms or outcomes. If our primary conclusions are similar with and without extreme missing data assumptions, confidence in the findings will be higher.

**Primary Aim.** Our primary aim is to examine feasibility and acceptability of the safety planning intervention to inform next-step study design. **Feasibility** of a larger future trial will be evaluated based on: a) enrollment rates for the research project (target = 70%), and feasibility of the intervention, b) the percentage of participants who complete the entire intervention protocol (target = 70%). We will also determine the appropriateness of our assessment battery for a larger, future trial, by examining whether the range of responses to instruments indicate sufficient variability and change over time. **Acceptability** will be demonstrated by study withdrawal (< 20%) and > 80% of the responses on a consumer satisfaction scale rated as highly satisfactory. We will use logistic regression to model binary outcomes of enrollment, completion of the protocol, and withdrawal as a function of treatment assignment. We will use ordinal logistic regression for the satisfaction scale analysis.

With respect to youth level clinical outcomes, the goal is to obtain a reasonably precise estimate of the standard deviation for the outcome variables, and pre-post correlations of outcome variables, which are essential statistics for powering a definitive trial. Following Leon et al (2011) and Kraemer et al (2006), our goal is not to obtain a preliminary estimate of the treatment effect size, but as per Teare and colleagues (2014), the size of the pilot we propose is sufficient to obtain sufficiently precise estimates of key variance and covariance parameters necessary to design a definitive trial. Our approach will be to conduct an analysis consistent with the testing of the hypothesis that JJS youth enrolled in the experimental condition have less self-injurious ideation and behavior at 1 and 3 month follow-up relative to youth enrolled in standard practice. We will also examine mechanisms including treatment attendance, safety skill acquisition, motivation for

treatment, and treatment barrier reduction. The main outcomes are suicidal ideation and suicide attempts/NSSI on the SITBI.

We will use generalized linear mixed models to test hypotheses that participants randomized to the safety plan condition will have significantly improved outcomes compared with those who receive standard practice. This approach accommodates varying numbers of observations across individuals (allowing the inclusion of all randomized participants) while controlling for within-subject correlation. Scores from continuous measures are the dependent variables and treatment condition is the primary independent variable. Analyses will also be conducted co-varying baseline SITBI scores. These hypotheses will be evaluated by regressing the outcome variables as observed on the 1 and 3-month follow-ups on treatment condition, and a time by treatment condition interaction in a general linear mixed effect modeling framework. Main inferences will be based on post-hoc omnibus tests of treatment group effects pooled over time points, and secondary inferences will be drawn from the time-specific outcomes.

The current study also seeks to illuminate factors that may better guide treatment decision making by identifying those who are most likely to benefit from the proposed interventions. Specifically, in exploratory analyses, we will examine sex, race, and ethnicity to address the barrier of racial disparities.

**Power:** We will recruit 70 participants in the RCT which should be sufficient to make judgments regarding feasibility and acceptability. We do not have pilot data available for calculating effect sizes to present here because R34 applications do not require pilot data but are used to collect pilot data regarding feasibility and acceptability. Two-way comparisons across treatment groups result in 80% power to detect effect sizes amounting to standardized mean differences (Cohen's d) of 1.0 or higher as statistically significant under a two-sample t-test analytic framework. With repeated measures for outcomes, under assumptions of reasonable reliability for the outcomes ( $r = .8$ ) and high autocorrelation for repeated measures ( $r = .64$ ), we will be able to detect smaller differences ( $d = .62$ ) in pairwise comparisons (where  $.62 = (16*(1-.8^2)/15)^{0.5}$ , following Lehr [137]). A medium ES when power is set at .8, is typically considered a clinically relevant finding. Thus, if high levels of feasibility and acceptability are found, this would suggest that the protocol should be tested in a larger trial. For power of .8 and a clinically relevant ES, i.e., a medium ES ( $d = .5$ ), a sample of 64 per group would be required in a future R01.

**Aim 2: Service level mechanisms** will be examined as potential mediators of intervention effects. Success of treatment linkage, including barriers to outpatient treatment, and the equity of intervention fidelity and treatment linkage across sex, race, and ethnicity will be compared following the analytic approach summarized in Aim 1.

